1. BACKGROUND

1.1 Epidemiology and burden of the condition

Over 50,000 people die each year following an out of hospital cardiac arrest (OHCA) in the UK(1, 2). Although initial resuscitation efforts restart the heart in about 25-30% of resuscitation attempts, most of these patients die in the next few days in hospital from severe brain damage(3) and overall survival (of attempted resuscitations) is less than 10%(1). Cardiac arrest causes a major burden on NHS resources (emergency treatment, post resuscitation care, rehabilitation) but treatment currently has a low chance of success.

The drug adrenaline has been an integral component of advanced life support from the birth of modern cardiopulmonary resuscitation in the early 1960s. In guidelines written originally in 1961, Peter Safar recommended the use of very large doses of adrenaline: 10 mg intravenously or 0.5 mg intracardiac(4). Animal studies show that injection of adrenaline during cardiac arrest increases aortic tone and thereby augments coronary blood flow(5, 6). However there are limited reliable data to assess the effects of adrenaline on long-term outcomes after cardiac arrest.

The International Liaison Committee for Resuscitation (ILCOR) synthesized the available evidence for adrenaline in 2010 (also re-assessed October 2012) and noted whilst it may improve the return of spontaneous circulation (ROSC) and short-term survival, there is insufficient evidence to suggest that adrenaline improves survival to discharge from hospital and neurological outcome. ILCOR stated that placebo-controlled trials to evaluate the use of any vasopressor in adult and paediatric cardiac arrest are needed(7).

[figure not shown]
1.1.1 Summary of clinical evidence

A Cochrane review led by our collaborator (8) identified a single randomised, placebo controlled trial of intravenous adrenaline in OHCA (Search run Dec 2012). The PACA trial(9), conducted by our co-investigators [name] & [name], was undertaken in Western Australia. The study aimed to enrol 5000 patients but at the time the study closed, only 601 patients had been randomised. The relatively small numbers led to the results having large uncertainty. The rate of ROSC [short term survival] was higher in those receiving adrenaline (64/272 (23.5%) vs. 22/262 (8.4%); OR 3.4, 95% CI 2.0 – 5.6), but there was not clear evidence of a benefit in survival to hospital discharge [long term survival]: adrenaline 11 (4.0%) vs. placebo 5 (1.9%) (OR 2.2, 95% CI 0.7 – 6.3). Two of the survivors in the adrenaline arm but none in the placebo arm had poor neurological outcome. In addition to the study's imprecision, interpretation of the findings is limited by a high level of post randomisation exclusions (n=67, 11%).

A second randomised study, conducted in Oslo, Norway compared intravenous (IV) cannulation and injection of drugs (including adrenaline) versus no IV cannula or drugs amongst 851 patients with OHCA(10). The patients in the IV group had better short-term survival (ROSC 165/418 (40%) vs. 107/433 (25%), OR 1.99, 95% CI 1.48-2.67)), however there was no clear difference in long term survival outcomes (survival to hospital discharge (IV arm 44/418 (10.5%) vs. no IV arm 40/433 (9.2%) OR 1.16 (95%CI 0.74-1.82); or favourable neurological outcome (Cerebral Performance Category [CPC] 1-2: IV 9.8% vs. no IV 8.1% OR 1.24 (0.77-1.98). The higher rate of ROSC was seen mainly in the patients with initial non-shockable rhythms (asystole and PEA): 29% vs. 11%. The rate of ROSC was 59% vs. 53% in those patients with an initial rhythm of VF/VT.

Observational studies enable large quantities of data to be collected but are often limited by selection bias, information bias and confounding. Statistical adjustment is often used to compensate for this, however unknown confounders may still lead to biased results. In a recent systematic review, we identified 16 observational studies comparing adrenaline use to no adrenaline use, including studies of adults and children in both in and out of hospital settings. Adrenaline fairly consistently improved short-term outcomes (4/5 studies reporting improved ROSC, OR range 0.86-2.24). The effect on long term outcomes was less certain (8/10 studies reported worse long term survival (OR range 0.09 – 1.98) and worse neurologically intact survival (3 of 3 studies, OR range 0.4 – 0.67) (11).

Figure 1 Estimates of survival to hospital discharge or long-term survival from observational studies comparing adrenaline with no adrenaline

In the post hoc analysis of the IV versus no IV trial, outcomes were examined according to whether the patient had actually received adrenaline(12). Treatment with adrenaline (n = 367) was associated with a greater chance of being admitted to hospital (OR 2.5; 95% CI 1.9 - 3.4). However long term survival outcomes were worse, with reduced survival to hospital discharge (adrenaline 24/367 (7%) vs. no adrenaline 60/481 (13%); OR 0.5; 95% CI 0.3 – 0.8) and reduced neurologically intact (CPC 1 or 2) survival (adrenaline 19/367 (5%) vs. no adrenaline 57/481 (11%); OR 0.4; 95% CI 0.2 - 0.7). These effects persisted after adjustment for confounding factors (VF, response interval, witnessed arrest, gender, age and tracheal intubation).

Three other recent studies in particular have suggested that adrenaline may cause worse long term outcomes. The largest observational study of adrenaline cardiac arrest involves 417,188 OHCA in Japan(13). In propensity-matched patients, use of adrenaline was associated with increased rate of ROSC (adjusted OR 2.51; 95% CI 2.24 – 2.80) but a 1-month survival rate approximately half of that achieved in those not given adrenaline (adjusted OR 0.54; 95% CI 0.43 – 0.68). In another observational study from the Osaka group in Japan(14). 1013 (32.0%) of 3161 patients analysed received adrenaline. Those receiving adrenaline had a significantly lower rate of neurologically intact (CPC 1 or 2) one-month survival than those not receiving adrenaline (4.1% vs. 6.1% OR 0.69; 95% CI 0.48 - 0.98)).

An analysis of registry data has shown reduced survival in those who received adrenaline; The North American Resuscitation Outcomes Consortium (ROC) Epistry (n=16,000) found an inverse association between epinephrine dose and survival to discharge (survival >20% for those not requiring adrenaline, falling to < 5% for those requiring more than two doses. This finding persisted after

adjustment for age, gender, EMS witnessed arrest, bystander witnessed arrest, bystander CPR, shockable initial rhythm, time from 911 to EMS arrival, the duration of OHCA and study site(15). This was similar to a previous analysis of the Swedish Registry (n=10,000; odds ratio long term survival 0.43, CI 0.27-0.66)(16).

This creates the paradox of better short term survival at the cost of worse long term outcomes, in other words a “double edged sword”(17).

1.1.2 Mechanisms by which adrenaline may cause harm

There are a number of mechanisms through which adrenaline may cause harm. These can be considered under the following headings:

1.1.2.1 Reduced micro-vascular blood flow and exacerbation of cerebral injury

In animal models of cardiac arrest, adrenaline increases coronary perfusion pressure (which predicts restarting the heart) but impairs macro and micro-vascular cerebral blood flow. Specifically adrenaline is noted to reduce carotid blood flow(18), micro-vascular blood flow(19), causing worsening cerebral ischaemia(20).

1.1.2.2 Cardiovascular toxicity

In a further analysis of the Norwegian IV versus no IV trial(10), adrenaline increased the frequency of transitions from PEA to ROSC and extended the time window for ROSC but at a cost of greater cardiovascular instability after ROSC, with a higher rate of re-arresting. These observations are consistent with other studies which link adrenaline with ventricular arrhythmias and increased post-ROSC myocardial dysfunction (21). In human studies with patients with sepsis (22) or acute lung injury (23), β agonist stimulation is similarly linked to cardiovascular instability and reduced survival (24). A systematic review of β blocker treatment in animal models of cardiac arrest found fewer shocks were required for defibrillation, myocardial oxygen demand was reduced and post resuscitation myocardial stability improved with less arrhythmia and improved survival(25).

1.1.2.3 Metabolic effects

Adrenaline causes lactic acidosis(26) which is associated with poor outcomes after cardiac arrest(27, 28). It also induces stress hyperglycaemia which is also associated with poorer outcomes (29).

1.1.2.4 Immunomodulation and predisposition to infection

Infective complications, including bacteraemia and early onset pneumonia are common after OHCA and associated with worse outcomes(30). The immune-modulatory effects of beta agonists have been well characterised and may reduce host defence to infection(31) which may contribute to an increased susceptibility to post resuscitation sepsis.

1.1.3 Summary of effects

Use of adrenaline in cardiac arrest increases short-term survival [ROSC] but there remains doubt whether this is translated into increased long-term outcomes. Observational studies suggest an association between adrenaline and worse long-term survival.

1.2 Research Question

Is the use of adrenaline in out of hospital cardiac arrest clinically and cost effective?

[figure not shown]
1.3 Need for a trial

Whether the practice of giving adrenaline is effective or not therefore remains an important question that needs to be answered. Uncertainty about adrenaline has been raised by recent evidence suggesting that it may be harmful. Resolution of this uncertainty is urgent, as adrenaline is used widely to treat cardiac arrests, and if harmful, may be responsible for many avoidable deaths. There are several precedents where treatments have been evaluated after years or decades of use and have been found to be ineffective or harmful, including pulmonary artery catheters in intensive care(32), beta agonists for acute respiratory distress syndrome (ARDS)(23) and corticosteroids for head injury(32). It is possible that adrenaline for cardiac arrest may be a similar case.

The International Liaison Committee on Resuscitation appraised the evidence surrounding adrenaline in OHCA in 2010(7) and again in Oct 2012 (Vienna, 2012). They concluded there is an urgent need for randomised, placebo controlled trials of adrenaline.

To assess attitudes of the UK clinical community we conducted a written survey of 213 attendees (doctors, nurses, paramedics) at the Resuscitation Council (UK) Annual Scientific Symposium in September 2012 to assess the scientific and clinical communities' current perspectives on the role of adrenaline for the treatment of cardiac arrest. Respondents expressed their agreement to a series of statements on a 7 point Likert scale (1 = strongly disagree, 7 strongly agree). Respondents reported that adrenaline increased short term survival (median score 6 (IQR 6-7)), but disagreed that it improved long term outcomes (median score 2 (IQR 2-3)). There was greatest uncertainty about the balance of risks and benefits of IV adrenaline (figure 2a). Respondents felt the most pressing future research need for the NHS was a trial comparing adrenaline to placebo (figure 2b).

Figure 2

A trial addressing this question is timely, because of the recent publication of studies questioning the effectiveness of adrenaline, and calls for a large scale randomised controlled trials (RCT) to resolve this issue. There are no other completed, on-going or planned trials in the clinicaltrials.gov or controlled-trials.com databases. Moreover, recent research projects (e.g. PARAMEDIC trial(33)) have shown the feasibility of conducting large scale OHCA trials in the UK. The learning from this trial, undertaken by this group, will help to ensure efficient and successful recruitment.

The emerging data suggest a number of experimental strategies could be considered including comparing adrenaline to alpha 2 agonists, adrenaline with beta blockade, lower dose adrenaline or adrenaline as a continuous infusion. The timing of adrenaline administration may also be important, however this is primarily dependent on ambulance response times which would be difficult to control for in a randomised trial. We suggest the most pressing need is for a definitive trial comparing standard dose adrenaline (1mg every 3-5 minutes) to placebo. Until there is clarity about the effect of adrenaline on long-term outcomes the best comparator agent (placebo or standard dose adrenaline) for trials of other agents remains unknown.

An RCT of adrenaline has the support of key stakeholders such as the College of Paramedics, Ambulance Medical Service Directors, Joint Royal College Ambulance Liaison Committee, Resuscitation Council (UK), patient representatives.

1.4 Good Clinical Practice

The trial will be carried out in accordance with the International Conference on Harmonisation (ICH) Good Clinical Practise (GCP), and applicable UK legislation, as well as WCTU Standard Operating Procedures (SOPs).

In the context of these guidelines adrenaline is considered the investigational medicinal product under investigation (the intervention).

2. TRIAL DESIGN

2.1 Trial summary

This is a pragmatic, individually randomised, double blind, controlled trial and economic evaluation.

[figure not shown]
Patients will be eligible if they are in cardiac arrest in the out-of-hospital environment and advanced life support is initiated. Exclusions are cardiac arrest as a result of anaphylaxis or life threatening asthma, patient known or appears to be under 16 and known or apparent pregnancy.

Patients will be randomised to either adrenaline (intervention) or placebo (control). Randomisation will occur when the trial IMP pack has been opened.

Outcomes are survival to 30 days (primary outcome), survival to hospital discharge, 3, 6 and 12 months, health related quality of life, health economics, neurological and cognitive outcomes (secondary outcomes).

All survivors will be contacted and invited to take part in the follow up (at 3 and 6 months).

Figure 3. Flow chart for PARAMEDIC-2 trial

2.1.1 Pilot Study

There will be an internal pilot to test that the components of this trial work together. The internal pilot will run for 6 months (from months 7-12). The data from the internal pilot will be included in the main trial. During the pilot we will measure recruitment rate, compliance with allocated intervention and that the approach to data collection and follow-up works effectively. It is intended to run seamlessly into the main trial.

The results of the pilot study will be reviewed with the TSC, DMC and representatives from the HTA specifically considering the achievement of the following targets:

- 25% of ambulance staff trained (i.e. majority (80%) participating staff at 25% of stations)
- 181 patients recruited within 6 months of first randomisation
- Data available on primary outcome >98%
- Proportion of patients who are alive agreeing to follow-up >75%
- Reconcile IMP packs with patients enrolled in the trial
- Review of our approach to inform patients and relatives of trial participation
- Review of feasibility to collect secondary outcomes

2.2 Objectives

2.2.1 Primary objective

The primary objective of this trial is to determine the clinical effectiveness of adrenaline in the treatment of OHCA measured as primary outcome: 30 day survival.

2.2.2 Secondary objective

Secondary objectives of the trial are to evaluate the effects of adrenaline on survival, cognitive and neurological outcomes of survivors and to establish the cost-effectiveness of using adrenaline.

2.3 Outcome Measures

2.3.1 Efficacy

Primary outcome:

Survival to 30 days post cardiac arrest.

Secondary outcomes:

1. Survived event (*sustained ROSC, with spontaneous circulation until admission and transfer of care to medical staff at the receiving hospital*)
2. Survival to hospital discharge (*the point at which the patient is discharged from the hospital acute care unit regardless of neurological status, outcome or destination*) 3, 6 and 12 months
3. Neurological outcome (modified Rankin Scale (mRS)) at hospital discharge, 3 and 6 months
4. Neurological outcomes (IQCODE and "Two simple questions") at 3 and 6 months
5. Health related quality of life at 3 and 6 months (SF12 and EQ-5D)
6. Cognitive outcome at 3 months (Mini Mental State Examination (MMSE))

7. Anxiety and depression at 3 months (Hospital Anxiety and Depression Scale (HADS))
8. Post Traumatic Stress at 3 months (PTSD civilian checklist (PCL-C))
9. Hospital length of stay
10. Intensive care length of stay

The outcomes defined by the Utstein convention for reporting outcomes from cardiac arrest (34) will be reported.

mRS will be measured at hospital discharge, 3 and 6 months. mRS was selected over Cerebral Performance Category (CPC) as it is more sensitive to detect mild cognitive impairment. It can be reliably extracted from medical records and is a predictor of long term survival. There is emerging international consensus (Utstein 2012/2013) that mRS should be the primary measure of neurological outcome in cardiac arrest trials. mRS is a 7 point scale ranging from mRS 0 (no symptoms) to 6 (dead). The spectrum of impairment of health related quality of life following cardiac arrest includes memory and cognitive dysfunction, affective disorders PTSD(35). The number of patients expected to survive to hospital discharge is anticipated to be in the region of 400-600, which will allow more intensive follow-up. The SF-12 is a standard quality of life measure that is short and easy to complete. In addition the EQ-5D will be used as a health utility measure for the health economic analysis.

Cognitive function will be assessed using the MMSE(36). The informant questionnaire cognitive decline evaluation (IQCODE) and the "Two Simple Questions" tool will form supplementary assessments of cognitive function. The PTSD Civilian Checklist (PCL-C)(37) is a 17-item self-administered questionnaire measuring the risk of developing PTSD and has been used in previous studies as a good surrogate for the clinical diagnosis of PTSD, which would require a face to face interview by a suitably trained professional. The HADS is a 14-item self administered questionnaire which has been previously used successfully to measure affective disorders in cardiac arrest survivors(38). Two of these measures (PCL-C and HADS) are being used as part of a multi-centre follow-up for people surviving a critical illness (Intensive Care Outcome Network (ICON) study), which can be used as a reference population(39).

2.3.2 Safety

There will be a system for reporting adverse events and serious adverse events in addition to the trial outcomes by participating ambulance clinicians (see Section 4).

See section 6.2 for information relating to interim analyses and early stopping criteria.

2.3.3 Health Economics

Primary Economic Outcome:

Incremental cost per quality-adjusted life year (QALY) gained from the perspective of the NHS and personal social services (PSS).

Secondary Economic Outcomes:

Cost of critical care stay (level 2/3 days); cost of hospital stay; utilisation of NHS and PSS resources after discharge; broader resource utilisation after discharge.

2.4 Sample Size

2.4.1 Incidence of primary outcome

Most existing data refer to survival to hospital discharge rather than survival to 30 days, but as most mortality will occur in the first days after cardiac arrest, we expect these two measures to be very similar. Estimates of long-term survival of patients who receive adrenaline during a resuscitation attempt vary between about 3.5% and 12%. From national data for England, overall survival to hospital discharge of patients for whom resuscitation is attempted is 7%(1). However, this will include a small number of patients who achieve ROSC immediately and would not receive adrenaline, hence would not be recruited to the trial. As these patients have much better outcomes, the survival among the trial population will be slightly lower. Estimates from the Norwegian trial of intravenous drugs and the Australian trial of adrenaline were 9%(10) and 4%(9) respectively. In the PARAMEDIC trial, survival for patients who received adrenaline is 6%, and in the REVIVE airways study, where most patients will have received adrenaline, it is 8.5% (personal communication [name]). We therefore expect survival to 30 days of approximately 6% in the adrenaline group.

The trial's primary aim is to estimate the treatment effect of adrenaline and the uncertainty around this; we have therefore based the target sample size primarily on the precision of the estimate of the risk ratio(40). Figure 4 shows the precision that is achievable (width of the 95% confidence interval for the risk ratio) with different total sample sizes, for risk ratios (placebo versus adrenaline) of 1.25 and 1.00. A risk ratio of 1.25 corresponds to an increase in 30-day survival from 6% in the adrenaline group to 7.5% in the placebo group.

[figure not shown]

Fig. 4. Width of 95% confidence interval for the risk ratio against sample size, for RR 1.25 (left) and RR 1.0 (right), with 6% survival in the adrenaline arm.

2.4.2 Sample size

The target sample size will be 8,000, which is expected to give a width of the 95% CI for the risk ratio of approximately 0.4 or slightly less; for a risk ratio of 1.25 the 95% CI is 1.07 to 1.46, and for risk ratio of 1.0 it is 0.84 to 1.19. There is a trade-off between precision and practicality in setting a target sample size; above 8,000, there is only a small improvement in precision, but the difficulty and time needed to recruit this number increase significantly. We expect a very small amount of missing data for survival outcomes; in PARAMEDIC we have ascertained survival status for over 99% of randomised patients, and we have therefore not adjusted the sample size estimates to account for missing data.

Using a conventional sample size calculation based on a significance test, a sample size of 8,000 would have 93% power to achieve a statistically significant ($p < 0.05$) result if the true treatment difference is a risk ratio of 1.33 (increase from 6% in adrenaline group to 8% in placebo group), or 75% power if the true treatment difference is a risk ratio of 1.25 (increase from 6% to 7.5%).

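### The expected 95% CI for a risk ratio of 1.25 in Section 2.4.2 should be 1.06 to 1.47, not 1.07 to 1.46; the target of 8,000 stands

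*Protocol*

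**What the plan says.** Section 2.4.1 of the protocol sets the basis of the design: "we have therefore based the target sample size primarily on the precision of the estimate of the risk ratio". It also fixes the inputs. The adrenaline arm is set by "We therefore expect survival to 30 days of approximately 6% in the adrenaline group", and the effect of interest by "A risk ratio of 1.25 corresponds to an increase in 30-day survival from 6% in the adrenaline group to 7.5% in the placebo group". The caption of Figure 4 repeats the same base rate: "for RR 1.25 (left) and RR 1.0 (right), with 6% survival in the adrenaline arm".

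Section 2.4.2 then gives the result. It opens with the size of the trial: "The target sample size will be 8,000". The precision claimed for that number is described as "expected to give a width of the 95% CI for the risk ratio of approximately 0.4 or slightly less". Two intervals illustrate this. For the effect of interest the section says "for a risk ratio of 1.25 the 95% CI is 1.07 to 1.46"; the case of no difference between the arms is covered by "for risk ratio of 1.0 it is 0.84 to 1.19". No allowance is made for missing data. The same section gives power of 75% for 6% v 7.5% and 93% for 6% v 8%.

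**The concern.** The two intervals stand side by side and should come from one formula, one sample size and one base rate. The interval for a risk ratio of 1.0 does follow from the stated inputs. The interval for 1.25 does not: it is narrower than 8,000 patients can give at 6% v 7.5%. Because the protocol puts precision ahead of power as its reason for 8,000, the wrong figure belongs to the main justification, and it is the only interval given for an effect other than no difference. At stake is whether a reader who checks the calculation can trust it.

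**Working it through.** **Inputs.** Total 8,000 (Section 2.4.2); survival 6% on adrenaline and 7.5% on placebo for a risk ratio (RR) of 1.25 (Section 2.4.1 and the Figure 4 caption); no inflation for missing data (Section 2.4.2). The protocol states no allocation ratio, so 1:1 is assumed, giving n = 4,000 per arm. Expected survivors are 240 on adrenaline and 300 on placebo.

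**Formula.** The usual log-scale interval: RR × exp(±1.96 × SE), with SE = sqrt[(1 − p1)/(n·p1) + (1 − p2)/(n·p2)]. The stated limits point to this scale, since sqrt(1.07 × 1.46) = 1.250.

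**Step 1: the companion interval, RR 1.0.** SE = sqrt(0.94/240 + 0.94/240) = 0.0885. The interval is 0.841 to 1.189, or 0.84 to 1.19, width 0.35. This matches the protocol.

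**Step 2: the disputed interval, RR 1.25.** SE = sqrt(0.925/300 + 0.94/240) = sqrt(0.00308 + 0.00392) = 0.0837. The interval is 1.25 × exp(±0.1640) = 1.061 to 1.473, or 1.06 to 1.47, width 0.41. The protocol has 1.07 to 1.46, width 0.39.

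**Step 3: could another method give the stated limits?** Same inputs throughout:

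| Method | 95% CI |
|---|---|
| Log-scale (Katz) | 1.061 to 1.473 |
| Koopman score | 1.061 to 1.473 |
| Test-based | 1.061 to 1.472 |
| Pooled SE | 1.062 to 1.471 |
| Walter (+0.5) | 1.061 to 1.472 |
| Poisson SE | 1.055 to 1.481 |
| Linear delta method | 1.045 to 1.455 |
| Odds ratio (1.27) | 1.07 to 1.51 |

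None gives 1.07 to 1.46.

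**Step 4: could another allocation?** Per patient, the variance terms are 0.94/0.06 = 15.667 and 0.925/0.075 = 12.333. The smallest SE over all splits of 8,000 is (sqrt 15.667 + sqrt 12.333)/sqrt 8,000 = 0.0835, which still gives 1.06 to 1.47.

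**Step 5: do the two stated intervals agree with each other?** With equal arms and these rates, the RR 1.0 interval rounds to the stated limits for totals from 7,586 to 8,354. The RR 1.25 interval does so for totals from 8,542 to 9,326. The ranges do not overlap, so no single sample size produces both.

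**Step 6: the power figures.** At 8,000, power for 6% v 7.5% is 76.2% (74.8% with continuity correction), against 75% stated. For 6% v 8% it is 93.9% (93.4% with correction), against 93% stated. Both fit 8,000. The stated interval for RR 1.25 implies SE = ln(1.46/1.07)/(2 × 1.96) = 0.0793, hence power of about Φ(0.2231/0.0793 − 1.96) = Φ(0.85), or 80%. That does not agree with the 75% in the same section.

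**The case against.** The strongest reply concerns weight. The design criterion is a width of about 0.4, the interval only illustrates it, and 0.41 is still about 0.4. The corrected interval still excludes 1, and the power figures hold. All of that stands, and it limits this to a numerical correction.

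Another reply is that 6% is a rounded figure. Survival of 6.4% v 8.0% at 8,000 gives 1.067 to 1.465, which rounds to the stated limits. But the text and the figure caption fix 6%, and at 6.4% the RR 1.0 interval becomes 0.846 to 1.182, which no longer rounds to the stated 0.84 to 1.19.

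Three stronger readings are tempting, and the protocol does not support them.

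- **That the trial is too small.** The unrounded limits 1.07 and 1.46 would need about 8,900 patients. The protocol does not make that interval a target. It presents 8,000 as a trade-off with little precision to gain beyond it, and the arithmetic agrees: width falls only from 0.412 at 8,000 to 0.397 at 8,600.
- **That the phrase allowing a width slightly below 0.4 is also wrong.** It introduces both scenarios, and fairly covers the RR 1.0 case, where the width is 0.35.
- **That the source of the slip is known.** Using 7.5% in both variance terms gives 1.072 to 1.458, which rounds to the stated limits, but this is only a guess.

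**Conclusion.** The stated interval for a risk ratio of 1.25 is wrong on the protocol's own inputs. It should be 1.06 to 1.47, width 0.41 instead of 0.39. Each limit is off by 0.01, and both errors make the design look slightly more precise than it is. The conclusion rests on 6% v 7.5% survival, 8,000 patients analysed and, for the exact limits, equal allocation; no other allocation gives the stated figure. Any missing outcomes would widen the interval, not narrow it.

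The correction is worth making because the figure is part of the main justification for the sample size. It does not show a shortfall in recruitment, a loss of power or a fault in the design. Figure 4 is not visible here, so nothing can be said about whether its panel for 1.25 carries the same error.

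**What to change.** In Section 2.4.2, replace the two illustrative intervals with: *With 8,000 patients, RR 1.25 has an expected 95% interval from 1.06 to 1.47 (width 0.41); RR 1.0 has one from 0.84 to 1.19 (width 0.35).* Check that the RR 1.25 panel of Figure 4 uses the same calculation, and redraw it if it does not. Keep the target of 8,000, the power statements and the description of the width as they are.

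The cost is one sentence and one check of a figure, with a stated precision that is slightly less favourable.
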